#### **4.5. Screening/Run-in Failures**

If a blood sample has been collected and it is determined that the subject does not meet the inclusion and exclusion criteria for participation in the study, then the investigator must withdraw those subjects and complete the appropriate documentation to request sample destruction within the timeframe specified by GSK.

### **5. STUDY TREATMENTS**

#### **5.1. Investigational Product and Other Study Treatment**

Tenofovir disoproxil fumarate (9-[(R)-2-[[bis[[[(isopropoxy-carbonyl) oxy] methoxy] phosphinyl] methoxy] propyl] adenine fumarate (1:1)); GS4331-05) is an oral pro-drug (bisPOC-PMPA) of tenofovir (PMPA), an acyclic nucleoside phosphonate (nucleotide) analogue of adenosine 5'-monophosphate. Tenofovir disoproxil fumarate has demonstrated antiviral activity against HBV and HIV and is indicated for use in combination with other antiretroviral agents in the treatment of HIV infection.

Tenofovir disoproxil fumarate tablets are white, almond-shaped, film-coated tablets containing 300 mg of TDF, debossed with “GSK” and “300” on one side of the tablet. Each tablet contains the following inactive ingredients: microcrystalline cellulose, lactose monohydrate, pregelatinised starch, croscarmellose sodium, and magnesium stearate. The tablets are film coated with Opadry II White 32K18425.

Study drugs (TDF) are packaged in white, high-density polyethylene bottles with a white child resistant cap. There are 30 tablets per bottle. Each bottle also contains silica gel canister(s) to protect the product from humidity and fibre packing to protect the product during handling and shipping.

For subjects who experienced virological breakthrough or partial virological response will add another drug without cross resistant to Tenofovir including LAM (Heptodin, GlaxoSmithKline, 100mg QD), ETV (Baraclude, Bristol-Myers Squibb, 0.5mg QD) and LdT (Sebivo, Novartis, 600mg QD). Investigator will make the decision for the drug selection.

#### **5.1.1. Handling and Storage of Investigational Product**

No preparation of investigational product is required at site.

The contents of the label will be in accordance with all applicable regulatory requirements.

Under normal conditions of handling and administration, investigational product is not expected to pose significant safety risks to site staff. A Material Safety Data Sheet (MSDS) describing the occupational hazards and recommended handling precautions will be provided to site staff if required by local laws or will otherwise be available from GSK upon request.

Investigational product must be stored in a secure area under the appropriate physical conditions for the product at lower than 25° C. Access to and administration of the investigational product will be limited to the investigator and authorised site staff. Investigational product must be dispensed or administered only to subjects enrolled in the study and in accordance with the protocol.

#### **5.1.2. Dosage and Administration**

Subjects will be assigned to receive open-label TDF 300 mg treatments for 240 weeks in the study. Subjects will be instructed to take one pill once daily. Investigational product absorption is not affected by food intake so the tablets do not have to be taken with a meal.

Subjects who receive add-on rescue treatment may take LAM 100 mg, ETV 0.5 mg or LdT 600 mg per day upon investigator's decision in addition to TDF tablet.

Subjects will be dispensed study drug at all visits except for the Week 240 or early study drug discontinuation visit. Subjects will be instructed to return unused study medication in the original container at each post-baseline study visit. The Investigator will be responsible for maintaining accurate records for all study drug and study drug bottles dispensed and returned. The inventory must be available for inspection by the study monitor. Study medication supplies, including partially used or empty bottles, must be accounted for and the dispensing logs must be verified by the study monitor prior to destruction or return.

If subjects develop renal insufficiency (defined by serum creatinine clearance) during study treatment, the following dose reduction criteria should be used when subjects have a serum creatinine clearance of <50 mL/minute:

Calculated Creatinine Clearance (mL/minute) a			Requiring Haemodialysis
≥ 50	30–49	10–29	
Tenofovir disoproxil fumarate 300 mg every 24 h	Tenofovir disoproxil fumarate 300 mg every 48 h	Tenofovir disoproxil fumarate 300 mg every 72 h	Tenofovir disoproxil fumarate 300 mg every 7 days or after a total of approximately 12 h of dialysis b
Lamivudine 100 mg every 24 h	Lamivudine is prohibited in such patients.		
Entecavir 0.5 mg every 24 h	Entecavir 0.5 mg every 48 h	Entecavir 0.5 mg every 72 h	Entecavir 0.5 mg every 5-7 days post-haemodialysis c
Telbivudine 600mg every 24 h	Telbivudine 600mg every 48 h	Telbivudine 600mg every 72 h	Telbivudine 600mg every 96 h or after dialysis c

a. Calculated using ideal (lean) body weight.

b. Generally once weekly assuming three haemodialysis sessions a week of approximately 4 h duration. Medication should be administered following completion of dialysis.

c. Medication should be administered following completion of dialysis.

## 5.2. Treatment Assignment

This is an open label, single arm study.

## 5.3. Blinding

N/A

## 5.4. Product Accountability

In accordance with local regulatory requirements, the investigator, designated site staff, or head of the medical institution (where applicable) must document the amount of investigational product dispensed and/or administered to study subjects, the amount returned by study subjects, and the amount received from and returned to GSK, when applicable. Product accountability records must be maintained throughout the course of the study.

## **5.5. Treatment Compliance**

The importance of compliance with the treatment regimen will be emphasised at each visit.

The subject must be reminded to return all unused medication (including empty containers). The Investigator or designated study site personnel should count the number of tablets returned by the subject to establish the number of tablets used, and compare this to the number of tablets expected to be used for the period. A record of this reconciliation must be maintained using the accountability forms provided, and any issues of non-compliance discussed with the subject.

## **5.6. Concomitant Medications and Non-Drug Therapies**

### **5.6.1. Permitted Medications and Non-Drug Therapies**

All concomitant medication and the reason(s) for their use must be entered into the CRF. Effort should be made to give only medications which are clearly indicated for a specific medical reason.

### **5.6.2. Prohibited Medications and Non-Drug Therapies**

No other investigational drugs, immunosuppressive therapy, immunomodulatory therapy (including IFN or thymosin  $\alpha$ ), systemic cytotoxic agents, chronic antiviral agents(e.g., LAM, adefovir, ETV, LdT, other medicinal products containing tenofovir, ganciclovir, famciclovir, FTC, DAPD, LFMAU, HBIg), agents containing glycyrrhizic acid(e.g., compound glycyrrhizin, compound ammonium glycyrrhetate, diammonium glycyrrhizinate), agents containing bicyclol or bifendate will be permitted, unless defined in protocol .

TDF should be avoided with concurrent or recent use of a nephrotoxic agent including but are not limited to cidofovir, acyclovir, valacyclovir, ganciclovir, valganciclovir, aminoglycosides (e.g., gentamicin), high-dose or multiple NSAIDs, and herbal medications (e.g., tripterygium wilfordii, leonuri and plant medicine containing aristolochic acid).

Traditional Chinese medicines and other herbal medicines intended to improve/protect liver function are prohibited during the study and must be discontinued at the time of screening. Such medicines include, but are not restricted to, oxymatrine and agents containing schisandra. Medicines intended to improve liver fibrosis are prohibited during the study and must be discontinued at the time of screening. Such medicines include, but are not restricted to, Fuzheng Huayu Capsule.

In the events mentioned in Section 6.3.1, medicines intended to improve/protect liver function will be allowed based on the Investigator's judgement after consulting with the GlaxoSmithKline medical monitor. All concomitant medication and reasons for their use

must be entered into the CRF. However, agents containing bicyclol, bifendate or schisandra will not be permitted in any situation.

### **5.7. Treatment after the End of the Study**

No post-study medication is provided as part of this protocol.

Discontinuation of anti-HBV therapy, including VIREAD, may be associated with severe acute exacerbations of hepatitis and must only take place under careful supervision.

The investigator is responsible for ensuring that consideration has been given to the post-study care of the patient's medical condition whether or not GSK is providing specific post study treatment. TDF study medication is commercially available in China.

### **5.8. Treatment of Study Treatment Overdose**

If a subject in the study takes an overdose, whether intentional or otherwise, the subject will be referred to a hospital at the Investigator's discretion. Management of such a subject should be symptomatic and supportive. In these circumstances it is the responsibility of the Investigator to obtain as much clinical data as possible, including blood samples for TDF or LAM/LdT/ETV assay, and to communicate this to GlaxoSmithKline. An SAE form must be completed if the overdose is associated with any signs or symptoms. For the purposes of this study, an overdose will be defined as any dose administration exceeded the recommended dose of TDF 300 mg, LAM 100mg, LdT 600mg or ETV 0.5mg per day.

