### **1.3.1. Risk Assessment**

Potential Risk of Clinical Significance	Data/Rationale for Risk	Mitigation Strategy
Investigational Product (IP)		
Renal toxicity	Tenofovir is principally eliminated by the kidney. Renal impairment, including cases of acute renal failure and Fanconi syndrome (renal tubular injury with severe hypophosphatemia), has been reported with the use of VIREAD.	
 
• Exclusion of CHB patients with creatinine clearance <70 mL/min
 
• Monitor renal function every 12 weeks
 
• Dosing interval adjustment of VIREAD is recommended in all patients with creatinine clearance below 50 mL/min.
 
• Stopping criteria based on renal function with serum creatinine confirms >2.5 mg/dL have been clearly defined.(see section 6.3.2)
 

Bone events	Decreases in Bone mineral density (BMD) has been reported in adults and pediatric patients. The effects of VIREAD-associated changes in BMD and biochemical markers on long-term bone health and future fracture risk are unknown.	
 
• Monitoring the serum calcium and phosphate every 12 weeks
 
• In every regular visits, the information of bone related symptoms will be collected.
 
• Assessment of BMD and related treatment should be considered by the investigator's judgement.
 

Lactic acidosis/severe hepatomegaly with steatosis and lipodystrophy	Lactic acidosis/ severe hepatomegaly with steatosis, including fatal cases, have been reported with the use of nucleoside analogs, including VIREAD, in combination with other antiretrovirals.	
 
• Guidelines for management of lactic acidosis are outlined in Appendix 4.
 

Drug-Drug Interaction Potential	Since tenofovir is primarily eliminated by the kidneys, coadministration of VIREAD with drugs that reduce renal function or compete for active tubular secretion may increase	
 
• Estimated creatinine clearance will be assessed in all patients every 12 weeks during treatment with TDF
 
• TDF should be avoided
 

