Confirmation of HBV DNA test will require an additional visit to collect serum sample. To receive rescue treatment subjects must have investigational product (IP) compliance  $>$  80% in the last regular visits period (usually 12 weeks). Add-on combination with a nucleoside agent (LAM, ETV or LdT) is acceptable rescue treatment in this study, as to investigator's decision. Before rescue treatment, serum sample should be collected for resistance testing.

Subjects who reach primary endpoint (i.e. develop liver complications or HCC) may withdraw from study. Investigator and subjects can decide whether to continue study drug. Subjects who continue to take study drug will be followed as per the original schedule until Week 240. During the follow-up period, AEs, concomitant medication, vital signs, hepatitis B virus DNA, haematology, chemistry and prothrombin will be evaluated. Serum/plasma storage also will be conducted.

Supplementary study conduct information not mandated to be present in this protocol is provided in the accompanying Study Procedures Manual (SPM). The SPM will provide the site personnel with administrative and detailed technical information that does not affect subject safety.

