#### **4.4. Withdrawal Criteria**

Should a subject fail to attend the clinic for a required study visit, the site should attempt to contact the subject and re-schedule the missed visit as soon as possible. The site should also counsel the subject on the importance of maintaining the assigned visit schedule and ascertain whether or not the subject wishes to and/or should continue in the study based on previous non-compliance. In cases where the subject does not return for the rescheduled visit or cannot be reached to reschedule the missed visit, the site should make every effort to regain contact with the subject (3 telephone calls and if necessary a certified letter to the subject's last known mailing address) so that they can appropriately be withdrawn from the study. These contact attempts should be documented in the subject's medical record. Should the subject continue to be unreachable, then and only

then will he/she be considered to have withdrawn from the study with a primary reason of “Lost to Follow-up”. For all other subjects withdrawing from the study, an alternative reason for discontinuation should be recorded in the eCRF.

Subjects who temporarily interrupted treatment for <28 consecutive days were allowed to continue in the study. Subjects with treatment interruptions of  $\geq 28$  consecutive days were required to withdraw from the study.

A subject may voluntarily discontinue participation in this study at any time. The investigator also have the right to withdraw patients from treatment or the study in the event of intercurrent illness, adverse events, protocol violations, administrative reasons or other reasons at any time. Any female subject who becomes pregnant while participating should withdraw from the study. The reason for withdrawal from the study must be recorded in the case report form (CRF).

Subjects will also be withdrawn from the study if they reached primary end-point. These subjects will be eligible for study drugs and originally scheduled follow-up.

Subjects who have received at least one dose of study drug and permanently discontinued the study drug should be followed up by the investigator as described in Table 1.

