### 6.2.3. Clinical Endpoint

The cumulative incidence of disease progression during the study timepoints will be defined as the first occurrence of any one of the following criteria:

- an increase in Childs-Pugh score (as defined in section 11.1 Appendix 1) of 2 or more points from baseline.
- An increase in Childs-Pugh score of 2 or more points, solely based on laboratory parameters (i.e. bilirubin, prothrombin time and/or albumin), confirmed at two consecutive visits at least one month apart;
- spontaneous bacterial peritonitis (with proven sepsis);

- renal insufficiency defined as a decrease in creatinine clearance to  $\leq 50$  mL/minute confirmed on two occasions at least one week apart (calculated from serum creatinine concentration);
- bleeding gastric/oesophageal varices;
- hepatocellular carcinoma;
- liver-related death

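### The overdose rule in Protocol 5.8 uses fixed daily amounts and ignores the longer dosing intervals of 5.1.2, so repeated daily dosing after a renal interval change is not an overdose

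*Protocol*

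**What the plan says.** Protocol 5.8 sets one daily overdose threshold for all subjects: "an overdose will be defined as any dose administration exceeded the recommended dose of TDF 300 mg, LAM 100mg, LdT 600mg or ETV 0.5mg". It does not mention renal function or 5.1.2. An overdose leads to referral to hospital at the investigator's discretion, blood for drug assay where possible, and communication to the sponsor. In addition, "An SAE form must be completed if the overdose is associated with any signs or symptoms".

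Protocol 5.1.2 gives one tablet daily as the standard regimen. Below 50 mL/min it changes the interval and not the tablet: "Tenofovir disoproxil fumarate 300 mg every 48 h" at 30-49 mL/min and "Tenofovir disoproxil fumarate 300 mg every 72 h" at 10-29 mL/min. Entecavir and telbivudine follow the same two steps, and lamivudine is prohibited. The risk table in 1.3.1 lists this as a mitigation for renal toxicity: "Dosing interval adjustment of VIREAD is recommended in all patients with creatinine clearance below 50 mL/min".

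The protocol foresees subjects in this range. Section 6.2.3 counts as disease progression "renal insufficiency defined as a decrease in creatinine clearance to" 50 mL/min or less, confirmed on two occasions. On reaching an endpoint, "Investigator and subjects can decide whether to continue study drug" (3.1). Section 4.4 says that such subjects are withdrawn from the study, but adds: "These subjects will be eligible for study drugs and originally scheduled follow-up".

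**The concern.** Below 50 mL/min the recommended daily amount in 5.8 is no longer the dose that the protocol assigns. A subject moved to 48 h or 72 h dosing who keeps the old habit of one tablet a day exceeds the assigned dose every time the interval is broken, yet exactly meets the 5.8 limit and does not pass it.

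These are the subjects in whom excess tenofovir matters most, because the drug is cleared by the kidney and interval adjustment is the stated protection. The steps specific to 5.8 would not be triggered for them. Section 6.3.3.1 says that overdose in itself is not reported as an AE or SAE unless it is intentional with possible self-harming intent. Section 5.8 is therefore the specific route by which an unintentional, symptom-free overdose reaches the sponsor.

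**Working it through.** The plan states no figure on this point, so there is none to reproduce. The check has four steps.

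**1. Ratio of daily dosing to the assigned dose.** Ratio = assigned interval / 24 h, with intervals from 5.1.2.

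| Clearance (mL/min) | Interval | Ratio | TDF taken vs assigned (mg/day) | ETV (mg/day) | LdT (mg/day) |
|---|---|---|---|---|---|
| 30-49 | 48 h | 48/24 = 2 | 300 vs 150 | 0.5 vs 0.25 | 600 vs 300 |
| 10-29 | 72 h | 72/24 = 3 | 300 vs 100 | 0.5 vs 0.17 | 600 vs 200 |

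Against the 5.8 threshold the ratio is 300/300 = 1, which does not exceed it. Lamivudine has no longer interval. Below 50 mL/min, continued lamivudine 100 mg a day also escapes 5.8, but as a prohibited drug and not as a multiple of an assigned dose.

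**2. Can each band be reached before study drug is stopped?** Section 6.3.2 stops all study drugs at confirmed creatinine above 2.5 mg/dL. The formula in Protocol Appendix 2 is clearance = (140 - age) x ideal weight / (72 x creatinine), times 0.85 for women. The ages and heights below are assumptions.

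- Man, 50 years, 170 cm: ideal weight 65.9 kg. At 2.5 mg/dL, clearance = 90 x 65.9 / 180 = 33.0 mL/min. He can reach the 2-times band. The stop comes before the 3-times band.
- Woman, 50 years, 160 cm: ideal weight 52.4 kg. At 2.5 mg/dL, clearance = 0.85 x 90 x 52.4 / 180 = 22.3 mL/min. Both bands are reachable.

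The result depends on build and age. A 60 kg man is at 33.3 mL/min at age 40 and 26.7 at age 60 (weight assumed).

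**3. How far must clearance fall, and would weekly monitoring catch it?** Entry requires at least 70 mL/min (4.3). Reaching 49 is a fall of (70 - 49)/70 = 30% from the lowest permitted baseline, or (100 - 49)/100 = 51% from a baseline of 100. Section 6.3.2 recommends weekly creatinine monitoring once creatinine is 0.5 mg/dL above baseline. From a baseline of 70 mL/min:

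- Man: creatinine 1.18 mg/dL at baseline and 1.68 at 49 mL/min, a rise of 0.50. The trigger falls at 49.1 mL/min.
- Woman: 0.80 at baseline and 1.14 at 49 mL/min, a rise of 0.34. The trigger falls only at 43.0 mL/min.

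The woman could thus be between 43 and 49 mL/min, assigned 48 h dosing, without weekly monitoring.

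**4. Size of the excess.** Visits are 12 weeks (84 days) apart.

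- Ceiling: 84 tablets against 42 assigned (42 extra) or 28 assigned (56 extra).
- If weekly monitoring led to correction within 7 days (assumption): 7 - 3.5 = 3.5 or 7 - 2.33 = 4.67 extra tablets.
- If bottles of 30 were dispensed to match the interval (assumption; quantities per visit are not stated): at most 60/42 = 1.4 times or 30/28 = 1.1 times.

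**The case against.** The strongest reply is that 5.8 handles acute events, and that a tablet of the right strength taken on the wrong interval is a dosing error which other sections already cover. Much of this stands.

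- Section 6.3.3.1 treats a noxious or unintended response at any dose as an adverse drug reaction, and 6.3.10 requires adverse drug reactions to reach the sponsor within 5 days. Section 6.3.10.1 asks for prompt notice of non-serious treatment-related events, and SAEs go within 24 hours. Drug-related symptoms need no overdose label to be reported.
- Tablets are counted against the expected number (5.5) and reconciled at each visit (Table 1). SAP 7.3.2 defines compliance as actual over expected intake per protocol. If the expected amount follows 5.1.2, daily dosing would show as about 200% or 300%. SAP 7.1 has a deviation category for wrong dose.
- The confirmed endpoint at 50 mL/min or less prompts a decision on study drug.

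A reader might therefore infer that nothing is lost. That goes too far. Tablet counts lead to discussion with the subject, and the SAP items are analysis summaries. None of them triggers assay blood or the 5.8 report.

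A reader might equally infer that over-dosing in these subjects would go unseen, or that 5.8 and 5.1.2 contradict each other. The documents support neither. The excess is visible by the routes above, and a subject can comply with both sections. It could also be argued that the recommended dose in 5.8 means the renally adjusted dose, but the sentence fixes it in milligrams per day.

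**Conclusion.** The point holds as a narrow gap in a safety definition. For a subject kept on drug after an interval change, 5.8 does not count 2 times the assigned dose as an overdose. Three times should not be read as the general case: it applies only where clearance falls below 30 mL/min before the creatinine stop. The larger multiples that the haemodialysis column would imply are not a realistic case, because study drug would normally have been stopped by then.

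The loss is limited to the overdose report for unintentional asymptomatic cases, the assay sample, and the SAE form for symptoms that are not otherwise serious. It requires a fall in clearance of at least 30%, continued study drug, and continued daily intake despite a longer assigned interval. The documents give no rate for that combination, so the number affected is small and may be zero. No endpoint, estimate, sample size or stopping rule changes. This is a worthwhile clarification and not a flaw that threatens the trial. The ratios follow directly from 5.1.2. The reachability and monitoring examples rest on the assumed ages and body sizes.

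**What to change.** In 5.8, define overdose as intake above the dose assigned under 5.1.2 for the subject's current renal function:

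- At clearance of 50 mL/min or more, keep the present daily limits.
- Once an adjusted interval applies, count more than one dose within the assigned interval on repeated occasions as an overdose. A single early tablet is excepted.
- Report any lamivudine taken after clearance is known to be below 50 mL/min in the same way.

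Tying the rule to the interval is better than a limit on cumulative intake. Under a cumulative limit, missed doses could hide a real excess, and two extra tablets spread over months could count as an overdose.

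The cost is about one sentence of protocol text and one line of site training. The downside is a few more overdose reports, some with assay blood or an SAE form. The single-tablet exception keeps one mistimed dose from causing these.
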